2.6.2 Safety

Safety analyses will be summarized for the safety set and by dose level of sabatolimab (400 mg Q4W, 800 mg Q4W) and for all participants ("All participants" column).

Safety summaries (tables, figures) include only data from the on-treatment period with the exception of baseline data which will also be summarized where appropriate (e.g. change from baseline summaries). In addition, a separate summary for death including on treatment and post treatment deaths will be provided. In particular, tables for adverse events (AEs) will summarize only on-treatment events, with a start date during the on-treatment period (treatment-emergent AEs).

The overall observation period will be divided into three mutually exclusive segments:

- 1. Pre-treatment period: from the day of participant's informed consent to the day before first administration of study treatment
- 2. On-treatment period: from date of first administration of study treatment to 30 days after the date of last administration of study treatment
- 3. Post-treatment period: any observation starting at day 31 after the last administration of study treatment

An overall safety period will be defined from date of first administration of study treatment to 150 days after the last dose of sabatolimab.

2.6.2.1 Adverse events (AEs)

AE summaries will include all AEs occurring during on-treatment period (until 30 days after last administration of study treatment). When specified, some AEs summaries will include all AEs occurring during the overall safety period.

Summary tables for adverse events (AEs) will include only AEs that started or worsened during the on-treatment period. The number (and percentage) of participants with treatment emergent AEs will be summarized by primary system organ class, preferred term and maximum severity (based on CTCAE grades).

All AEs reported in the AE eCRF page will be listed along with the information collected on those AEs, e.g. toxicity grade, relationship to study treatment, outcome, action taken etc. AEs that started during the pre-treatment, post-treatment and after the overall safety period will be flagged in listings.

AEs will be summarized by number and percentage of participants having at least one AE, having at least one AE in each primary system organ class (SOC) and for each preferred term (PT). A participant with multiple occurrences of an AE will be counted only once in the respective AE category. A participant with multiple CTCAE grades for the same preferred term will be summarized under the maximum CTCAE grade recorded for the event. AEs will be assessed according to the Common Terminology Criteria for Adverse Events (CTCAE) version 5.0

In the AE summaries, the primary system organ class will be presented alphabetically and the preferred terms will be sorted within primary SOC in descending frequency. The sort order for the preferred term will be based on their frequency in the sabatolimab 800 mg Q4W. The summaries will show 'All grades' (including AEs with missing grade) and 'Grades \geq 3'.

The following adverse event summaries will be produced selecting all or a subset of AEs depending on seriousness, relationship to study treatment, outcome or action taken:

- AEs (all AEs (by SOC and by PT) and separately those considered related to study treatment
- SAEs and separately those considered related to study treatment
- SAEs with number of occurrences (an occurrence is defined as > 1 day between start and prior end date of record of same preferred term).
- Non-SAEs

Novartis	For business use only	Page 33 of 46
Statistical Analysis Plan (SAP)		MBG453B12203

- SAEs with fatal outcome and separately those considered related to study treatment
- AEs leading to study treatment or sabatolimab discontinuation
- Related to study treatment AEs leading to study treatment discontinuation
- AEs leading to dose adjustment/interruption for sabatolimab, venetoclax or azacitidine
- AEs requiring additional therapy
- COVID-19 related adverse events by MedDRA COVID-19 (SMQ) terms.

In addition, all AEs and SAE by SOC and PT will be also provided for the overall safety period. Adverse events for the safety follow up period (day 31-150 after last dose of sabatolimab) will be described by system organ class and preferred term.

Separate summaries for on-treatment and all deaths (including post-treatment deaths not in the AE CRF but in the survival CRF) will be produced showing reason for deaths by SOC and preferred term. All AEs, deaths, and serious adverse events (including those from the pre- and post-treatment periods) will be listed and those collected during the pre-treatment, posttreatment and overall safety period will be flagged in listings. A separate listing of deaths prior to starting treatment will be provided for all screened participants.

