Hospitalizations ²⁰								
Antineoplastic therapies, HSCT and transfusions since discontinuation of study treatment						Cor	ntinuous	
Disposition					Х		Х	
Survival Follow-up								Х

^x Assessment to be recorded in the clinical database or received electronically from a vendor
 ^s Assessment to be recorded in the source documentation only
 ¹ The last assessment of bone marrow and/or peripheral blood counts should be used within 28 days prior to enrollment.
 ² Blood transfusions administered within 16 weeks prior to the first dose will be collected and recorded in the eCRF.
 ³ Blood chemistry should be confirmed within 72 hours prior to planned first dose.

\sim	C 1	
(:0	ntid	ential
-	inua	Cincia

Period	Treatment			End of Treatment	Safety Follow-up	Efficacy Follow-up	Survival Follow-up	
Cycle	Cycle 6	6 Cycle 7 (and subsequent cycles)						
Visit Name	D28	D1	D8	D28	EOT	30, 90, 150 day	Every 12 weeks until Disease Progression	Every 3 months
Days	D28	D1	D8	D28	EOT	30, 90, 150 days	Every 12 weeks	Every 12 weeks

⁴ Cytogenetics to be performed locally. Assessment to be recorded in the clinical database (eCRF)

⁵ Any deficiency should be corrected before the start of Study Treatment. Refer to Table 8-3 for details on analytes to be tested.

⁶ Refer to Section 6.5.4.3 for DILI follow-up

⁷ Only GLDH to be tested at baseline - see Table 8-7

⁸ This test will be performed only for women of child bearing potential

⁹ Does not need to be performed if it was done in screening within 72 hours before first dose

¹⁰ Refer to Section 8.4.2 for detailed guidance on timepoints

¹¹ Venetoclax will be dispensed via IRT on Day 1 of each Cycle. Azacitidine will be dispensed via IRT daily as per standard clinical practices.

¹² See Section 8.3.1 for details on response assessments

¹³ See Table 8-9 for detailed PK/IG sampling timepoints and schedule

¹⁴ See Table 8-10 for detailed timepoints and collection schedule for venetoclax PK sampling. Venetoclax PK sampling will be collected during Phase 1 (safety run-in) only.

¹⁷ PROs will be collected during Phase 2 (expansion) only

²⁰ Hospitalization is required at Cycle 1 from Day 1 to Day 3 for subjects participating to the Safety run-in Part. Chemistry will be collected on pre-dose Day 1, Day 2 and Day 3 for TLS monitoring.

²¹ If the patient begins new antineoplastic medication before the end of the safety follow-up period, then only suspected AEs and suspected SAEs will continue to be collected. See Section 10.1

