9.1.1.1 Safety follow-up

All participants must be followed for safety for 150 days after the last dose of sabatolimab or 30 days after the last dose of azacitidine or venetoclax whichever is longer.

After the 30-Day on-site safety follow-up visit, participants will be followed via telephone call (or on-site visit if participant happens to be visiting the site) at 90 and 150 days after the last dose of sabatolimab. All safety assessments should be completed as per Table 8-1. However, if the participant begins new antineoplastic medication before the end of the safety follow-up period, the collection of new SAEs and AEs unrelated to study medication will stop and thereafter only suspected AEs and suspected SAEs will continue to be collected up to the end of the safety follow-up period. For female participants of childbearing potential, a pregnancy test will be performed at the timepoints listed in Table 8-1.

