If the event worsens the event should be reported a second time in the CRF noting the start date when the event worsens in toxicity. For grade 3 and 4 adverse events only, if improvement to a lower grade is determined a new entry for this event should be reported in the CRF noting the start date when the event improved from having been Grade 3 or Grade 4.

Conditions that were already present at the time of informed consent should be recorded in medical history of the participant.

Adverse event monitoring should be continued for at least:

 \cdot 150 days after the last administration of sabatolimab, or 30 days after the last administration of azacitidine, or 30 days after the last administration of venetoclax, whichever is later.

OR

 \cdot until the start of a new post treatment antineoplastic medication if sooner than the 150 days mentioned above. If a participant starts post treatment antineoplastic medication, then only adverse events suspected to be related to study treatment should be collected, up to 150 days after discontinuation of sabatolimab.

Adverse events (including lab abnormalities that constitute AEs) should be described using a diagnosis whenever possible, rather than individual underlying signs and symptoms. When a clear diagnosis cannot be identified, each sign or symptom should be reported as separate adverse event.

Once an adverse event is detected, it must be followed until its resolution or until it is judged to be permanent (e.g. continuing at the end of the study), and assessment must be made at each visit (or more frequently, if necessary) of any changes in severity, the suspected relationship to the interventions required to treat it, and the outcome.

Adverse events separate from the progression of malignancy (i.e. deep vein thrombosis at the time of progression or hemoptysis concurrent with finding of disease progression) will be reported as per usual guidelines used for such events with proper attribution regarding relatedness to the drug.

Information about adverse drug reactions for the investigational drug can be found in the Investigator's Brochure (IB).

Abnormal laboratory values or test results constitute adverse events only if they fulfill at least one of the following criteria:

- they induce clinical signs or symptoms
- · they are considered clinically significant
- · they require therapy

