10.1.3 SAE reporting

To ensure participant safety, every SAE, regardless of causality, occurring after the participant has provided informed consent and until the end of the safety follow-up period (Section 9.1.1.1), must be reported to Novartis safety within 24 hours of learning of its occurrence. Detailed instructions regarding the submission process and requirements are to be found in the investigator folder provided to each site.

SAE reporting timeframes:

1. Screen Failures (e.g. a participant who is screened but is not treated): All SAEs occurring after the participant has provided informed consent until the time the participant is deemed a Screen Failure must be reported to Novartis.

2. Treated participants SAEs collected between time participant signs ICF until 30 days after the participant has discontinued or stopped azacitidine or venetoclax or 150 days after stopping sabatolimab, whichever is later. If a participant starts post treatment antineoplastic medication, then only SAEs suspected to be related to study treatment must be collected, up to 150 days or beyond after discontinuation of sabatolimab.

All follow-up information for the SAE including information on complications, progression of the initial SAE and recurrent episodes must be reported as follow-up to the original episode immediately, without undue delay, and under no circumstances later than within 24 hours of the investigator receiving the follow-up information. An SAE occurring at a different time interval or otherwise considered completely unrelated to a previously reported one must be reported separately as a new event.

If the SAE is not previously documented in the Investigator's Brochure or Package Insert (new occurrence) and is thought to be related to the study treatment, a CMO & PS Department associate may urgently require further information from the investigator for health authority reporting. Novartis may need to issue an Investigator Notification (IN) to inform all investigators involved in any study with the same study treatment that this SAE has been reported.

Suspected Unexpected Serious Adverse Reactions (SUSARs) will be collected and reported to the competent authorities and relevant ethics committees in accordance with EU Guidance 2011/C 172/01 or as per national regulatory requirements in participating countries.

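### The SAP's all-causality AE tables to day 150 include time after a new antineoplastic drug, when the protocol collects only suspected events

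*SAP*

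**What the plan says.** **Collection.** Protocol 9.1.1.1 covers a participant who begins new antineoplastic medication during safety follow-up: "the collection of new SAEs and AEs unrelated to study medication will stop and thereafter only suspected AEs" and suspected SAEs continue to the end of that period. Section 10.1.1 gives the same rule for AEs ("If a participant starts post treatment antineoplastic medication, then only adverse events suspected to be related to study treatment should be collected"). Section 10.1.3 gives it for SAEs ("then only SAEs suspected to be related to study treatment must be collected"), and footnote 21 of Table 8-1 repeats it ("then only suspected AEs and suspected SAEs will continue to be collected"). The opening sentence of 10.1.3 is broader. It asks for every SAE to be reported, whatever its cause, through the end of safety follow-up.

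**Tabulation.** SAP 2.6.2 defines the overall safety period as first dose of study treatment to 150 days after the last sabatolimab dose. SAP 2.6.2.1 plans that "all AEs and SAE by SOC and PT will be also provided for the overall safety period". It continues: "Adverse events for the safety follow up period (day 31-150 after last dose of sabatolimab) will be described by system organ class and preferred term". The splits for treatment-related events appear in the list of on-treatment summaries and are not specified for these two additional tables. SAP 2.1 takes percentages over all participants in the relevant population.

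**The concern.** A participant who moves to another therapy stays in the denominator to day 150, but from the switch onward unrelated events no longer reach the database. A table labelled as all AEs then combines two ascertainment rules without saying so.

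Switching is foreseeable. Protocol 6.1.5.1 does not permit treatment beyond progression, so some participants can be expected to need other therapy. The SAP already deals with new antineoplastic therapy for the duration endpoints, EFS, PFS and LFS, but the AE section has no matching rule or caveat.

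At stake is how a reader interprets late toxicity. A low all-causality figure for days 31-150 could be taken as few events when part of it reflects events that were not collected.

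**Working it through.** The documents state no post-treatment AE incidence and no share starting new therapy, so there is no plan figure to reproduce. The check has three parts.

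**1. Rules side by side**

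| Time | Collected (protocol) | Tabulated (SAP 2.6.2.1) |
|---|---|---|
| Before new therapy | All AEs and SAEs | All AEs and SAEs |
| New therapy to day 150 | Suspected AEs and SAEs only | All AEs and SAEs, same denominator |

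The numerator can only lose events in the second row and the denominator does not change. The tabulated percentage is therefore equal to or below the one under full collection, and equal if nobody switches. The overall-period table is affected less, because SAP 2.6.2.1 counts a participant once per AE category and someone already counted on treatment is not lost.

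**2. Illustration for days 31-150 (120 days)**

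All inputs are assumptions:
- P: share with at least one AE under full collection (0.40 or 0.70)
- s: share of AEs that are suspected (0.10 to 0.30)
- f: share starting new therapy (0.20 to 0.60)
- t: start day after the last sabatolimab dose (31 to 90)

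With a constant hazard, a switcher has effective collection time x = (t - 31) + s(151 - t). The chance that a switcher is counted is p = 1 - (1 - P)^(x/120). The tabulated share is (1 - f)P + f·p.

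| P | s | f | t | x | p | Tabulated | Shortfall (points) |
|---|---|---|---|---|---|---|---|
| 0.40 | 0.3 | 0.2 | 90 | 77.3 | 0.280 | 37.6% | 2.4 |
| 0.40 | 0.1 | 0.4 | 60 | 38.1 | 0.150 | 30.0% | 10.0 |
| 0.40 | 0.1 | 0.6 | 31 | 12.0 | 0.050 | 19.0% | 21.0 |
| 0.70 | 0.3 | 0.2 | 90 | 77.3 | 0.540 | 66.8% | 3.2 |
| 0.70 | 0.1 | 0.6 | 31 | 12.0 | 0.113 | 34.8% | 35.2 |

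Over this grid the shortfall is 2.4 to 35.2 percentage points. For the planned Part 1 size of about 18 that is 18 × 0.024 = 0.4 to 18 × 0.352 = 6.3 participants. At f = 0 it is zero.

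**3. Does a date cut alone repair it?**

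Take P = 0.40, f = 0.4, t = 60. Dropping every event after the switch gives p = 1 - 0.6^(29/120) = 0.116. The crude percentage is then 0.6 × 0.40 + 0.4 × 0.116 = 28.6%, which is lower than the 30.0% above because the suspected events are dropped too.

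A person-time rate over the same cut recovers the target. The daily hazard is -ln(0.6)/120 = 0.004257. Mean time to first event or cut is 0.40/0.004257 = 94.0 days for non-switchers and 0.116/0.004257 = 27.3 days for switchers, so 0.6 × 94.0 + 0.4 × 27.3 = 67.3 days overall. The rate is 0.2865/67.3 = 0.004257 per day, which is 40% over 120 days. This holds if switching is unrelated to AE risk.

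**The case against.** The strongest reply is that little depends on these two tables. They are supplementary and descriptive, and the main AE summaries are on-treatment, to 30 days after the last study treatment. The Part 1 primary endpoint is DLTs in the first two cycles. Suspected events are still collected, and the all-deaths summary draws on the survival CRF. Every AE is listed with its relationship to treatment and period flags, and post-treatment antineoplastics are summarized. Recruitment has stopped, the report is an abbreviated CSR, and a planned Part 1 of about 18 can be read case by case. All of this stands and limits the severity.

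Three further replies also stand:
- The shortfall is conditional on someone switching before day 150, and the documents do not say how many do.
- The day 31-150 window runs from the last sabatolimab dose, and participants may continue azacitidine or venetoclax alone. The window can therefore overlap the on-treatment period, so setting the two tables against each other is not a clean contrast in any case.
- The opening sentence of protocol 10.1.3 can be read as keeping all-cause SAE collection. The narrower rule later in that section, with 9.1.1.1 and footnote 21, points the other way, but the text needs reconciling.

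It can also be argued that events during the next therapy are not of interest. That supports a cut at new therapy. It does not support a table that covers the time and collects only part of the events.

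**Conclusion.** The collection and tabulation rules do not match, and the SAP does not resolve this elsewhere. If any participant starts new antineoplastic therapy before day 150, the all-causality percentages in the overall-period and day 31-150 tables are biased downward relative to full collection, with most of the effect in the latter. The size is unknown, and the ranges shown rest entirely on assumed inputs and a constant hazard. On-treatment tables are touched only if new therapy starts within 30 days of the last dose. DLT results, related-event counts and death summaries are largely or wholly unaffected.

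Two stronger readings are tempting. A reader might infer that late AE rates must fall by construction. The documents do not support that, because the loss is zero without switching and no switching figure is given. A reader might also infer that the 400 mg and 800 mg columns cannot be compared. Unequal switching could distort them, but the documents give no uptake by dose, and planned cohorts of about 6 and 12 allow little comparison anyway.

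Severity: minor.

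**What to change.** In SAP 2.6.2.1:

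- **Related events.** Add related AE and SAE tables for the overall safety period and for days 31-150. This is the only class collected under one rule to day 150.
- **All-causality events.** End these tables at the earlier of day 150 and the day before new antineoplastic therapy. State whether HSCT triggers the cut, since the safety follow-up rule speaks of medication and the SAP treats HSCT separately for the duration endpoints. Limit the day 31-150 denominator to participants still under all-causality collection at day 31. Report exposure-adjusted (person-time) rates, because a crude percentage with a cut is still understated.
- **Footnote.** State the collection rule under each table.

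In protocol 10.1.3, or a clarification to it, reconcile the opening sentence on SAEs of any cause with the later narrowing.

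The cost is SAP wording and a little extra programming. Dates of further antineoplastic therapy are already collected: SAP 2.4.2 summarizes these therapies and Table 4-2 lists their start and end dates as a data source.

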The date of first administration of any study treatment component (sabatolimab or azacitidine or venetoclax) is defined as the first date when a non-zero dose of the respective study drug is administered and recorded on the study treatment eCRF page.

Date of last administration of study treatment (sabatolimab or azacitidine or venetoclax)

The date of last administration of any study treatment component (sabatolimab or azacitidine or venetoclax) is defined as the last date when a non-zero dose of the respective study drug is administered and recorded on the study treatment eCRF page. So both, first and last date of study drug, are derived separately for each drug which is part of the study treatment.

Date of first administration of study treatment (combination)

The date of first administration of study treatment (or start date of study treatment) is defined as the first date when a non-zero dose of any component of the study treatment (sabatolimab, Azacitidine or venetoclax) is administered.

Date of last administration of study treatment (combination)

The date of last administration of study treatment (or start date of study treatment) is defined as the last date when the last non-zero dose of any last component of the study treatment (sabatolimab, Azacitidine or venetoclax) is administered.

Date of last exposure to study treatment component (sabatolimab or azacitidine or venetoclax)

One planned cycle length is 28 days and the start date of a cycle is defined as the first administration of azacitidine within a cycle. Azacitidine is planned to be administered daily every cycle during 7 days at the beginning of each cycle (between Day 1 to Day 9). Sabatolimab is administered every 4 weeks (Q4W), on Day 8 of each cycle, unless there was a toxicity leading to a dosing interval increase. Venetoclax is planned to be administered once a day from day 1 to day 14 of the 28-day cycle.

The date of last exposure to sabatolimab is therefore calculated as:

• Minimum (last date of administration of sabatolimab + 27 days, date of death, last contact date in case participant is lost to follow-up), as sabatolimab injections are given Q4W.

The date of last exposure to azacitidine is calculated as:

• Minimum (last date of administration of azacitidine + 20 days, date of death, last contact date in case participant is lost to follow-up) as the 7 doses of azacitidine are given in the beginning of each cycle.

The date of last exposure to venetoclax is calculated as:

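### The overall safety period is timed from sabatolimab alone, so it can close before the on-treatment period when another study drug runs more than 120 days longer, and the day 31-150 AE table includes on-treatment events

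*SAP*

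**What the plan says.** SAP 2.6.2 defines the on-treatment segment as follows: "On-treatment period: from date of first administration of study treatment to 30 days after the date of last administration of study treatment". SAP section 4 makes the end date depend on all three drugs, because last administration of the combination "is defined as the last date when the last non-zero dose of any last component of the study treatment" is given.

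The same SAP 2.6.2 then sets a further window: "An overall safety period will be defined from date of first administration of study treatment to 150 days after the last dose of sabatolimab". Protocol 12.5.2 has the same definition.

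SAP 2.6.2.1 uses that window in two ways. For tables, "all AEs and SAE by SOC and PT will be also provided for the overall safety period". For listings, "AEs that started during the pre-treatment, post-treatment and after the overall safety period will be flagged in listings". It also adds a table of "Adverse events for the safety follow up period (day 31-150 after last dose of sabatolimab". That table appears only in the SAP.

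The protocol's collection rule is wider. Section 9.1.1.1 follows participants for "150 days after the last dose of sabatolimab or 30 days after the last dose of azacitidine or venetoclax whichever is longer". Section 10.1.1 has the same rule, ending with "30 days after the last administration of venetoclax, whichever is later".

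**The concern.** The windows have different anchors. One follows the last dose of anything, while the other two follow the last dose of sabatolimab. The protocol allows the two dates to separate. Under section 6.5.3, a sabatolimab dose that misses its window in the cycle is skipped, and a participant who cannot tolerate one drug may continue on the others.

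Two effects follow, with very different thresholds.

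- **Overall period.** After a long enough gap, the period called overall ends before the on-treatment period. A treatment-emergent event can then be missing from the overall AE and SAE tables and be flagged in the listing as occurring after the overall period, although it was collected under the protocol's own rule.
- **Day 31-150 table.** Any dose of another drug after the last sabatolimab dose brings on-treatment events into a table titled as safety follow-up. A reader could take them for post-treatment events.

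Those affected include participants who stopped sabatolimab for toxicity and stayed on the other drugs.

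**Working it through.** The plan states no figure to reproduce, so the check is day counting on its own windows.

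**Inputs**
- S = day of last sabatolimab; planned on Day 8 of a 28-day cycle (SAP section 4).
- L = day of the last dose of any study drug. Venetoclax is planned to Day 14 (SAP section 4). Azacitidine is planned to Day 7, or to Day 9 on the alternative schedule (protocol 6.1.1).
- g = L − S, taken as 0 when sabatolimab is the last drug given.

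**Windows, measured from S**
- On-treatment ends at g + 30.
- Overall safety period ends at 150.
- Follow-up table covers days 31 to 150, which is 150 − 31 + 1 = 120 days.

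**Formulas**
- On-treatment days inside the follow-up table: min(g + 30, 150) − 31 + 1 = min(g, 120).
- On-treatment days after the overall period closes: max(0, g + 30 − 150) = max(0, g − 120).

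**Results.** Let m be the number of further undelayed 28-day cycles without sabatolimab. With venetoclax to Day 14, g = 28m + 14 − 8 = 28m + 6.

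| m | g (days) | Overlap with day 31-150 table | On-treatment days outside overall period |
|---|---|---|---|
| 0 | 6 | 6 | 0 |
| 1 | 34 | 34 | 0 |
| 2 | 62 | 62 | 0 |
| 3 | 90 | 90 | 0 |
| 4 | 118 | 118 | 0 |
| 5 | 146 | 120 (all) | 146 − 120 = 26 |
| 6 | 174 | 120 (all) | 174 − 120 = 54 |

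If the last dose is azacitidine on Day 9, g = 28m + 1: the overlap is 1 day at m = 0 and 113 at m = 4, and the days outside are 21 at m = 5 and 49 at m = 6. If the last dose is on Day 7, g = 28m − 1 for m of 1 or more: the overlap is 111 at m = 4, and the days outside are 19 at m = 5 and 47 at m = 6. At m = 0 the overlap is 0 if sabatolimab is the last drug given.

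**Worked case, m = 5 with venetoclax to Day 14.** On-treatment ends at S + 146 + 30 = S + 176, which is also the protocol's collection limit. The overall period closes at S + 150. Events starting on S + 151 to S + 176 are collected and treatment-emergent, yet lie outside the overall period.

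**No sabatolimab at all.** Azacitidine and venetoclax start on Day 1 and sabatolimab on Day 8, so a participant can be treated without reaching sabatolimab. The Safety Set needs only one dose of study treatment (SAP 2.2.2). The Full Analysis Set has the same one-dose rule, and SAP 2.2.1 explicitly foresees this case. S does not exist for such a participant, so neither sabatolimab-anchored window is defined.

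**The case against.** The strongest reply is that the 150-day window is deliberately about sabatolimab. It is the investigational drug, protocol 9.1.1.1 times the 90- and 150-day contacts from its last dose, and the SAP table names its anchor openly. A display of events arising 31 to 150 days after sabatolimab stops is coherent even while azacitidine or venetoclax continues.

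This stands for the follow-up table. A reader might infer that the table is meant to hold only events after all treatment has ended, but neither document says so. Re-anchoring it to the last dose of any drug would also have a cost: once g reaches 120 days, the participant would contribute no follow-up time and late events after stopping sabatolimab would not be shown separately. What remains is a labelling problem, because the title says safety follow-up while some events are on-treatment.

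The reply does not rescue the overall period. Keeping sabatolimab + 150 days as one limb is fine, but the protocol's own collection rule has a second limb that the definition omits.

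It is also fair to say that the three segments in SAP 2.6.2 do not contradict each other. Only pre-, on- and post-treatment are declared mutually exclusive, and the two windows at issue lie outside that partition. Every event on the AE page is listed, so none is lost from the report. SAP section 1 confines reporting to the safety run-in, planned at about 18 participants, where listings can settle individual cases.

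**Conclusion.** The point holds, as a minor one. The overall safety period has an end-date rule that can exclude collected on-treatment events once another drug continues more than 120 days after the last sabatolimab dose, and that gives no end date if sabatolimab was never given. The day 31-150 table includes on-treatment events after a gap of one day or more, but only up to 6 of 120 days when the final cycle runs as planned.

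Two stronger readings are not supported. One is that any later dose of another drug pushes events out of the overall period; up to four further undelayed cycles the number of days outside is zero. The other is that the trial's AE results are distorted. The main on-treatment AE tables use the any-component anchor and are correct as defined, and the DLT analysis and CR rate do not use these windows. The reach is the overall-period AE and SAE tables, one supplementary table and the listing flags.

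The day counts assume undelayed 28-day cycles, sabatolimab on Day 8, and events classified by start date. The documents do not say how often sabatolimab alone is skipped, stopped or never given, so the number of events affected cannot be estimated.

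**What to change.** - **SAP 2.6.2:** end the overall safety period at the later of last sabatolimab + 150 days and last dose of any component + 30 days, using the second limit alone if sabatolimab was never given. On-treatment days outside the period are then g + 30 − max(150, g + 30), which is never above zero.
- **SAP section 3:** record this as a departure from protocol 12.5.2, since the protocol has the same gap.
- **SAP 2.6.2.1:** keep the day 31-150 window, label it as time since last sabatolimab, and split or flag its events by whether they start within the on-treatment period or after it.

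The cost is one revised definition, one entry in section 3, and one extra split in a supplementary table, all before database lock. No new data are needed, because the protocol already collects adverse events to the later limit.
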